this stage will primarily be driven by the size and power requirements. Small form factor components, such as BGA (ball grid array) components, will be selected to miniaturize the electrical circuit sensor. The component efficiency will also be optimized and measured to be within the uA range. Initial mock-ups of all components using the breadboard will be completed. Development kit testing will also be performed to confirm the expected performance in operation components. The targeted sleep current is expected to be on the order of 10-20 uA with active measurement 100 to 200 uA depending on measurement frequency. Schematic capture. Brash will design the PCB circuits for the selected components. With an optimization focus towards size and power efficiency, Brash will avoid leakage through resistors and capacitors and design the FSR signal conditioning circuit to maximize signal quality in the expected force range. Placement and layout. The placement of each component on the PCB will be optimized to ensure the form factor will work when integrated into the night guard. This will require iteration of developing initial placement and PCB for factors, creating CAD mockups, evaluating if the design is manufacturable, and determining comfort for patients. The layout of the electrical routing of the signals will be designed to minimize EMC noise while maximizing EMI robustness as per IEC-60601 standards. Testing and iterations. Initial prototypes of the PCB will be tested to ensure core functionality, as well as to validate that the current consumption will meet expected targets. Components and PCB design will be adjusted depending on the results. A final version will then be integrated into a night guard for ex-vivo calibration and force testing followed by the pilot study in Aim 3. Electronic design validation. To validate the circuit design, the electronics must perform active measurements for 8 hrs within a 48-hr stand-by time. Brash will also investigate whether the circuit can store this compression force data locally, using the test jig, during this timeframe to be transferred via Bluetooth protocol. Brash will also ensure that the mechanical integration of the electronics and battery within the Otis custom night guard will not impede the night guard's functionality or the user's comfort.

**Milestone:** Miniaturized electric circuit board to meet the following metrics: 8 hours operations; 48 hours sleep time (standby time) of the device; standby currents 15-20 microamps current; operating current average ~100-200 microamps range (function of how often we are taking measurements)

**Problems and Solutions:** Optimizing the current consumption may be technically challenging as it requires a tight interplay between hardware and device firmware. If so, Brash will consider using microcontrollers for low-power applications to minimize the risk of hardware design errors that may result in higher current consumption. As an alternative, Brash might leverage existing firmware that can match the targeted current consumption rates. Secondly, Brash might find that after establishing a working form factor for integration with the night guard, the night guard may not properly fit over the patients' teeth nor fit their mouth geometry. To mitigate this risk, instead of integrating typically rigid and square-shaped PCB circuits, Brash will explore flexible PCBs or rigid-flex PCBs with multiple pieces. It is also unclear if an off-the-shelf FSR will have the ideal workable dimensions for integration, in which case a custom design may be required from the manufacturer (Tekscan).

**Aim 3: Conduct a usability pilot study with 28 patients to capture bite compression force profiles and optimize data collection.** Otis will determine whether the OBSNG prototype can reliably capture bite compression force data with participants. In summary, Otis will screen and recruit 28 participants (50/50 Male/Female; 14 with no/mild bruxism and 14 with moderate/severe bruxism) to wear the Otis Brux-Sensor Night Guard prototype for 21 days over a 6+ hour sleep period each night. [name] (lead PI) is a licensed dental hygienist with over 13 years of performing oral health screenings and will train each patient on how to use the device and perform the calibration step before each participant begins the study. Otis/Brash will confirm that the prototype can store the data, transmit it to the software, and analyze the data. Brash will analyze the data collected to determine whether the patient's jaw forces can be analyzed and replicate similar compression forces from the jig. Using this data, Brash/Otis will evaluate whether a trend difference can be identified between patients with no/mild bruxism compared to participants with moderate/severe bruxism. Brash/Otis will also evaluate whether the core functionality of the technology can measure forces while using the device to ensure measurements are repeatable within reasonable deviance. The study protocol will be reviewed and approved by an internal review board (IRB) (TBD).

**Procedure: Screening/recruitment:** Otis will recruit 28 participants to meet our recruitment criteria from the Otis Dental customer database. For recruitment, [name] will reach out via email to all Otis Dental customers who are currently wearing the Otis Custom Night Guard, and advertise an opportunity to be part of the study. All interested participants will reply to [name], who will then send them more information providing an overview and scope of the pilot study. Participants will fill out a screening survey to ensure they are willing to wear a custom night guard for 3 weeks (21 days), undergo an initial tele-dental health screening by [name] (licensed dental hygienist) before participating in the study, and have data collected from the sensor-enhanced custom night guard. Demographic background information (e.g., age, gender, race, health history, etc.) will also be collected at this time. To meet the eligibility criteria, participants must have access to a smartphone, be fluent English-speaking,

be 18 years of age or older, are healthy with no major underlying health challenges, and have a sleep regime of at least 6 hours. To ensure confidentiality, all participants will be assigned a random 3-digit number as an ID which they will be referred to throughout the study. All demographic data and data collected throughout the study will be securely stored in a Cloud and only accessible by Otis/Brash. All participants will be informed that their participation is voluntary and they can drop out any time. **Onboarding:** Once the 28 participants have been identified (50/50 Male/Female), [name] will perform a virtual (e.g., Zoom) oral health screening on each of the participants to identify any physical symptoms of bruxism and ensure they qualify to participate in the study. This includes an examination of the upper/lower dentition, gingival tissue, tongue, surrounding oral mucosa, jaw joints, and masticatory muscles. Here, [name] will evaluate the participant's physical wear on teeth, and have participants palpate the jaw and muscles to see if there is any clicking/popping for the misalignment of the joint. Since all participants are customers and have used the Otis custom night guard, [name] will also review each participant's digital records within the Otis database to ensure his health examination aligns with what is on file. Afterward, [name] will assess the Otis custom night guard to determine the level of wear based on current use. Using assessment from the oral health screening outcomes and Otis custom night guard wear, [name] will assign each participant to the no/mild bruxism or moderate/severe bruxism group according to **Table 1**.

Table 1. Parameters/Metrics to distinguish participants with no/mild Bruxism or moderate/severe Bruxism			
	Oral health screening assessment ( Anticipated physical symptoms of bruxism performed by [name] )	Qualitative bruxism assessment ( Baseline assessment before study – after 1 week of using the Otis custom night guard )	Anticipated quantitative assessment ( data collection after study completion – performed by Brash )
Participants with No/Mild Bruxism	Minimal-to-no physical wear on anterior teeth and/or posterior molars; Minimal-to-no clicking/popping and/or misalignment of the jaw joint; Minimal-to-no gum recession; Reported stress levels to be low/mild	Night guard shows mild wear after 1 week of use	Compression forces between 25-100N
Participants with Moderate/Severe Bruxism	Moderate-to-severe physical wear on anterior teeth and/or posterior molars; moderate-to-severe clicking/popping and/or misalignment of the jaw joint; moderate-to-severe gum recession; Reported stress levels to be moderate/high	The night guard shows significant wear after 1 week of use.	Compression forces between 100-200N

**Procedure:** Each participant that meets the screening criteria and is eligible to participate in the study will meet with [name] to receive a prototype of the OBSNG. [name] will provide both written and verbal instructions on how to use the OBSNG. [name] and [name] will also calibrate the device before first use by candidates, followed by another calibration, after the last use by the candidate. This will allow the team to determine any potential data discrepancies due to gradual wear throughout the utilization of the device. All participants will be asked to wear the Otis Brux-Sensor Night Guard before going to bed for 21 consecutive days. Here, participants will be instructed to (1) take the Otis Brux-Sensor Night Guard out of the storage case; (2) seat the device on their upper dentition; (3) sleep with the device on for a minimum of 6 hours; (4) clean the night guard with a tepid water rinse, after each use; (5) place the night guard back into the storage case and allow to air dry for next use). All who complete the study will be compensated with a \$100 Visa Gift card and they can keep the custom night guard (retail value of up to \$500). **Data analysis:** The team will begin averaging all compression force episodes throughout each of the 6+ hours of sleep per night and graph all 21 nights of averaged scores to show every candidate's Bruxism pattern during the study. The team will determine the bruxism severity (no/mild or mod/severe), based on the range of compression forces and validate each candidate's bruxism severity.

**Milestone:** > 90% of the prototypes can store data for the 21-day trial throughout the 6+ hour sleep period and transmit the data to the software; moderate/high bruxism participants having averaged compression forces 100 - 200 N) greater than the average compression bite force profiles to that of the no/mild bruxism participants (or 25-50% greater); agreement between oral assessment, physical nightguard wear, and compression forces according to **Table 1**; confirm reproducibility and accuracy of data collection by checking daily variability of bruxism patterns from both groups to determine if severe bruxer values (100 – 200 N compression force) are consistently higher than mild bruxers values (25 - 100 N of compression force), from night-to-night.

**Problems and Solutions:** If the sensor becomes damaged due to saliva and/or water cleaning, various dental adhesive materials will be tested to protect the sensor from damage, without jeopardizing nocturnal function.

**Statistics.** Upon Phase I completion, Otis will pursue a Phase II proposal to further optimize the prototype via a larger clinical study by analyzing varying severity levels of bruxism using statistical means and AI/ML techniques.

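### The guard-wear criterion for severity assumes one week of use, but it is applied to guards whose prior use is neither standardised nor recorded

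*Protocol*

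**What the plan says.** All places are in Protocol section 3.2, Aim 3.

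- **Screening/recruitment.** The invitation goes by email to "all Otis Dental customers who are currently wearing the Otis Custom Night Guard".
- **Onboarding.** The text repeats the point: "Since all participants are customers and have used the Otis custom night guard". The assessor is then to "assess the Otis custom night guard to determine the level of wear based on current use". Group assignment according to Table 1 follows directly: "Using assessment from the oral health screening outcomes and Otis custom night guard wear".
- **Table 1, header of the wear column.** "Baseline assessment before study – after 1 week of using the Otis custom night guard".
- **Table 1, no/mild row.** "Night guard shows mild wear after 1 week of use".
- **Table 1, moderate/severe row.** "The night guard shows significant wear after 1 week of use".
- **Milestone.** Success includes agreement between the oral assessment, the physical wear of the guard and the measured forces, judged by Table 1.

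The only device handed out in Aim 3 is the sensor prototype, and its handover is described after groups have been assigned.

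**The concern.** A wear grade carries information about severity only if exposure is the same for everyone or is taken into account. Table 1 fixes exposure at one week. The onboarding text grades whatever guard the participant has at the time, after however much use it has had. Two people with the same bite force but different guard ages could then receive different grades.

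Two things are at stake. First, wear is one of the two inputs to group assignment, so unequal exposure can blur the groups whose forces are to be compared. Second, wear is used again in the agreement milestone. If guard age drives part of the wear grade, disagreement between wear and force could come from the reference and not from the sensor, and the sponsor could not tell which. If guard age and use are not recorded before assignment, the analysis may be unable to correct for them later.

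**Working it through.** The protocol gives no figure of its own to reproduce here. The check is a comparison of the text, followed by two illustrations whose assumptions are not in the protocol.

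**1. Can the criterion be carried out as written?**

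| Needed by Table 1 | Provided in Aim 3 |
|---|---|
| Guard used for one week at grading | Guard already in use by a current customer; duration not stated |
| A one-week baseline before the study | No new standard guard and no run-in |
| Known exposure | No guard-age limit; no recording of purchase date or nights worn |

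Digital records are reviewed, but the stated purpose is to check that the health examination agrees with what is on file. The criterion therefore cannot be applied as written, except by chance to someone who started a week earlier.

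**2. Does wear build up with use?** The protocol itself treats it that way: the prototype is recalibrated after last use because of gradual wear, and that covers only 21 nights.

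**3. How much extra use might matter?** Assume that wear is proportional to force times weeks of use. The Table 1 anticipated forces are 25-100 N (no/mild, midpoint 62.5 N) and 100-200 N (moderate/severe, midpoint 150 N). A no/mild guard then shows the one-week wear of a moderate/severe guard after:

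- midpoints: 150 / 62.5 = 2.4 weeks
- shortest: 100 / 100 = 1 week
- longest: 200 / 25 = 8 weeks

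Under that assumption a few weeks of prior use would be enough.

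**4. Which way does the error go?** Against a one-week threshold, extra use only adds wear. It can push a no/mild participant up. A participant with severe bruxism and a new guard still meets the moderate/severe criterion. The main error is therefore one-way contamination of the moderate/severe group.

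**5. Effect on the force difference.** Let m be the share of the moderate/severe group who are misplaced no/mild participants, with each group at its Table 1 midpoint.

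- True gap: 150 − 62.5 = 87.5 N
- Observed gap: (1 − m) × 87.5
- m = 0.10: 0.90 × 87.5 = 78.75 N, about 79 N
- m = 0.20: 0.80 × 87.5 = 70 N

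In a group of 14, m of 0.10 to 0.20 is 1.4 to 2.8 people, so roughly one to three. Nothing in the protocol supports this rate; it only shows scale.

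**6. Against the milestone.** At m = 0.20 the moderate/severe mean is 62.5 + 70 = 132.5 N, and 132.5 / 62.5 = 2.12. That is still well above the alternative target of 25-50% greater. On these figures the exposure lies more in individual classification and the agreement milestone than in the difference between group means.

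**The case against.** The best case for the plan has four parts.

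- **The Table 1 header may imply a one-week baseline.** It does hint at one, so the fault may be a missing procedural step and not a decision to grade old guards on a one-week scale. But no procedure provides the week, and the onboarding wording points to the guard in current use. The inconsistency stands.
- **Oral screening dilutes the error.** Tooth wear, joint signs, gum recession and reported stress also enter the assignment, so a worn guard alone need not change a group. This stands as a limit on size. It does not remove the problem, because no rule says which input prevails when the two disagree.
- **Records may show guard age.** Possibly, but they are not reviewed for that purpose.
- **This is a 28-person usability pilot**, and statistical separation of severity levels is deferred to Phase II. That lowers the stakes, and the data storage and transmission milestone is untouched. The force-difference, agreement and night-to-night milestones still depend on the grouping.

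A reader might also infer more than the text supports. One inference is that every participant's guard is much older than a week and that severity will be misread. The protocol gives no guard ages; use is unstandardised, not shown to be long, and misreading is a risk. Another is that participants are swapped equally in both directions, which would give a factor of 1 − 2m and a gap of 52.5-70 N at the same 10-20%. That does not follow from extra wear against a fixed one-week threshold. It would need a further assumption, such as the assessor ranking guards against one another.

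**Conclusion.** The concern holds as an unreconciled criterion. Table 1 requires one week of use, while recruitment and onboarding supply guards with unstandardised and unrecorded use. Following the plan can confound duration of use with severity, both in the grouping and in the agreement milestone, and the likely direction is no/mild participants placed in the moderate/severe group.

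The size is unknown. The reduction from 87.5 N to about 70-79 N rests on an assumed 10-20% contamination and on group forces at the Table 1 midpoints; the figure of 2.4 weeks rests on assumed proportional wear. The contradiction in the text depends on none of these. Because the rule governs assignment, it has to be settled before the first participant is assigned and cannot be left to the analysis stage.

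**What to change.** Reconcile the recruitment text, the onboarding text and Table 1 before assignment, with one rule applied to all participants.

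- **Preferred.** At screening, record guard purchase date and nights of use per week. Grade wear relative to nights used. Reword the wear column of Table 1 and the agreement milestone to match. Cost: two screening questions and the rewording.
- **If use history is not reliable for all participants.** Assign everyone by oral screening alone, and report exposure-adjusted wear as a separate comparison where the history allows it. Do not drop wear for only some participants: that would create two assignment rules and leave the agreement milestone undefined for part of the sample.
- **Alternative.** Provide the baseline that the Table 1 header implies: a new standard guard for each candidate, graded after one week and before assignment. Cost: one guard per candidate and one week.

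Where wear stays in the assignment, the same edit should say how it is combined with the oral screening when the two disagree and, since the oral screening is virtual, how the guard is examined.

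### Aim 3 validates severity through an unsourced 100 N force cut, so its agreement milestone can fail when force tracks severity, and it conflicts with the 25–50% milestone

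*Protocol*

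**What the plan says.** All of this is in the Protocol, section 3.2, Aim 3.

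- **Design.** There are 28 participants, "14 with no/mild bruxism and 14 with moderate/severe bruxism". The licensed dental hygienist who screens them "will assign each participant to the no/mild bruxism or moderate/severe bruxism group according to" Table 1, using the oral screening and the wear on the existing night guard.
- **Question.** The team will "evaluate whether a trend difference can be identified between patients with no/mild bruxism compared to participants with moderate/severe bruxism".
- **Table 1, quantitative column.** For no/mild: "Compression forces between 25-100N". For moderate/severe: "Compression forces between 100-200N". The column is headed as anticipated, and no source is given for either band.
- **Data analysis.** Force is averaged per night and graphed over 21 nights. Then: "The team will determine the bruxism severity (no/mild or mod/severe), based on the range of compression forces and validate each candidate's bruxism severity".
- **Milestone.** One criterion is "agreement between oral assessment, physical nightguard wear, and compression forces according to" Table 1. Another compares the moderate/severe average with that of the "no/mild bruxism participants (or 25-50% greater"). A third checks that severe values stay above mild values from night to night.

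**The concern.** Force is recorded in newtons on up to 21 nights, but the per-participant validation and the force leg of the agreement milestone use only the band it falls in. Two participants at 99 N and 101 N count as opposite; two at 30 N and 99 N count as the same. The result therefore depends on where the two groups lie relative to 100 N, as well as on whether force rises with severity. If both groups lie mostly on one side, a sensor that ranks participants well would still be recorded as disagreeing with the clinical assessment.

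The question stated for Aim 3, whether a difference between the groups can be seen, needs no cut. The milestones also sit side by side without being reconciled, so the same data could pass the relative-difference criterion and fail the agreement criterion. The team would then have no rule for saying whether Phase I succeeded on this point.

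**Working it through.** The protocol gives no SD, test, alpha, agreement statistic or pass level, so there is no stated figure to reproduce.

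**Inputs from the protocol.** 14 participants per group; bands 25–100 N (midpoint 62.5 N) and 100–200 N (midpoint 150 N); a moderate/severe average 25–50% above no/mild as an accepted difference.

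**Assumed.** Participant mean forces are normal, with a common SD *s* in both groups. Values of 10 to 30 N are shown; 18.75 N is a quarter of the no/mild band width, (100 − 25)/4. The quantity classified is taken to be the participant's mean force.

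**Step 1: the two milestones set against each other (no SD needed).**
- From 62.5 N: 62.5 × 1.25 = 78.1 N and 62.5 × 1.50 = 93.75 N. Both lie in the no/mild band.
- The moderate/severe mean reaches 100 N only if the no/mild mean is at least 100/1.25 = 80 N (25% greater) or 100/1.50 = 66.7 N (50% greater).
- If force is symmetric within a group, a group mean below 100 N puts more than half of that group in the wrong band.

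**Step 2: expected agreement against discrimination.** With no/mild mean m₁ and moderate/severe mean m₂:
- Agreement = ½[Φ((100 − m₁)/s) + Φ((m₂ − 100)/s)]
- AUC (area under the ROC curve) = Φ((m₂ − m₁)/(s√2))
- With a 14/14 split, chance agreement is 50%, so kappa = 2 × agreement − 1.

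Worked case, 62.5 and 93.75 N, s = 18.75 N: agreement = ½[Φ(2.00) + Φ(−0.33)] = ½[0.977 + 0.369] = 0.67; kappa 0.35; AUC = Φ(31.25/26.52) = Φ(1.18) = 0.88. Only 37% of moderate/severe participants reach 100 N.

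| Means (N) | SD (N) | AUC | Agreement |
|---|---|---|---|
| 62.5 and 93.75 (50% greater) | 10 | 0.99 | 63% |
| 62.5 and 93.75 | 18.75 | 0.88 | 67% |
| 62.5 and 93.75 | 30 | 0.77 | 65–66% |
| 62.5 and 78.1 (25% greater) | 15 | 0.77 | 53% |
| 120 and 165 (all forces high) | 25 | 0.90 | 60% |
| 62.5 and 150 (Table 1 midpoints) | 20 | 1.00 | 98% |
| 62.5 and 150 | 30 | 0.98 | 92% |

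The first row shows the problem most clearly: separation is almost perfect, yet agreement is 63% because only 27% of moderate/severe participants reach 100 N. In the last two rows the cut does little harm.

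**Step 3: information lost by cutting force.** With the two clinical groups fixed, the efficiency of a cut placed *c* SDs from the centre, relative to the uncut normal value, is φ(c)²/[Φ(c)(1 − Φ(c))] (a large-sample result for small differences).
- c = 0: 0.64, so about 36% lost
- c = 0.5: 0.58, about 42% lost
- c = 1: 0.44, about 56% lost
- c = 1.5: 0.27, about 73% lost

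**The case against.** The other side has real weight.

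- **Continuous force is not abandoned.** Nightly averages are stored and graphed, and the group-average and night-to-night milestones compare force values. This stands. A reader might infer that the pilot leaves Phase II with no usable estimate of discrimination; the documents do not support that, because an AUC or another cut could be computed later from the stored data.
- **The loss is not always large.** A reader might infer that most of the information is lost. That is not general: it is about a third at a central cut, above half only when the cut is nearly 1 SD or more off centre, and very little discrimination is lost if the groups sit at the Table 1 midpoints.
- **No test is planned.** Comparing a t-test on newtons with Fisher's exact test at 100 N gives striking power figures (about 99% against 51% at 62.5 and 93.75 N, SD 18.75 N). The plan contains no such test and leaves formal statistics to Phase II, so those figures do not describe this milestone. The choice of agreement statistic may lie in an analysis plan that is not shown, and its absence is not the complaint.
- **A failed band match is itself informative.** It would show that the anticipated bands are wrong. True, but the protocol words this step as validating each candidate's severity, not as checking the bands.
- **The cut is partly inferred.** The bands share 100 N, leave forces below 25 N and above 200 N unclassed, and the summary to be classified is not named. This stands as a caveat.
- **A finer clinical grade is not part of the point.** Table 1 has two clinical levels, and nothing in the protocol supports splitting them.

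None of this removes the conflict in Step 1, which uses only the protocol's own numbers.

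**Conclusion.** The concern holds in a limited form. The per-participant validation and the force leg of the agreement milestone rest on an implied 100 N cut with no stated source. That milestone can fail while force tracks severity, and it can fail on data that meet the protocol's own 25–50% criterion. The second statement follows from the protocol's figures alone whenever the no/mild mean is below 66.7 N (50% greater) or 80 N (25% greater).

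The size depends on assumed SDs, normality and where the group means lie. With means of 62.5 and 93.75 N, agreement is about 67% against an AUC of 0.88 at SD 18.75 N, and about 63% against 0.99 at SD 10 N. At the Table 1 midpoints with SD up to about 30 N, agreement is 92% or more and there is little to gain. Since no agreement pass level is stated, whether 63–67% counts as failure is a judgement; against 50% by chance it would be hard to call validation. The change is worth making because the better measure uses data already collected.

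**What to change.** In Aim 3, Data analysis, and in the agreement criterion of the Aim 3 Milestone:

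1. Make the main validation each participant's mean force in newtons against the clinical group assigned at onboarding. Report the between-group difference and the area under the ROC curve, each with a 95% CI, with the participant as the unit.
2. Keep the match to the Table 1 bands as a descriptive secondary table.
3. Reconcile the 25–50% criterion with the Table 1 bands, so that one set of data cannot meet one and contradict the other.

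The cost is wording in two paragraphs. No participants, visits, measurements or staff are added, and the 14/14 recruitment split stays. The downside is that the simple yes/no match per participant becomes secondary, and with 14 per group the confidence intervals may be wide.

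### The device pass rate in the Aim 3 milestone counts storage and transmission only, so a prototype whose force sensor has failed still counts as a success

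*Protocol*

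**What the plan says.** All references are to the Protocol, section 3.2 Proposed Studies.

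- **Purpose.** The Aim 3 summary says the sponsor will "determine whether the OBSNG prototype can reliably capture bite compression force data with participants". The pilot has 28 participants, "14 with no/mild bruxism and 14 with moderate/severe bruxism".
- **Milestone, item 1.** More than 90% "of the prototypes can store data for the 21-day trial throughout the 6+ hour sleep period and transmit the data to the software".
- **Milestone, items 2 to 4.** Item 2 is a group contrast: "moderate/high bruxism participants having averaged compression forces 100 - 200 N" and above the no/mild group, or alternatively an excess of 25 to 50%. Item 3 is "agreement between oral assessment, physical nightguard wear, and compression forces according to" Table 1, with no threshold. Item 4 sets out to confirm reproducibility and accuracy by checking whether the severe group reads consistently higher than the mild group from night to night.
- **Calibration.** The Aim 3 Procedure calibrates each device before first use, "followed by another calibration, after the last use by the candidate", in order to find discrepancies caused by wear. It gives no acceptance limit and no consequence.
- **Foreseen failure.** Problems and Solutions begins "If the sensor becomes damaged due to saliva and/or water cleaning" and answers with tests of protective adhesives. It does not say whether a damaged prototype counts as a failure or how its data are handled.
- **Accuracy margin.** The Aim 1 milestone sets 10%-15% on the bench. Aim 3 does not carry it over.

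**The concern.** Item 1 has two inputs, storage and transmission. A sensor that has gone flat, saturated or lost sensitivity can still let the electronics write and send a complete record, so that prototype is counted as a success. Yet the question Aim 3 puts is about force, the protocol names a way in which the sensor may fail, and the devices are rinsed after each of 21 nights of use. The measurement that would reveal the failure is planned but feeds into no Aim 3 criterion.

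At stake is what the pilot can conclude about reliable force capture, and Phase II is to build on this prototype. A second effect is confusion of causes. A moderate/severe participant with a failing sensor may read below 100 N and then appear as a disagreement with Table 1, when the real cause is the device.

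**Working it through.** The protocol derives no sample size, power or error rate for the milestone, so there is no figure of its own to reproduce.

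**1. What the threshold means.** With 28 prototypes, 25/28 = 89.3% fails and 26/28 = 92.9% passes, so item 1 needs at least 26. As written, it places no limit on the number of failed sensors. If sensor function were part of it, at most 28 - 26 = 2 prototypes could fail.

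**2. Would items 2 to 4 catch general failure?** Suppose every sensor is dead and reads 0 N. Item 2 fails, since 0 N is below 100 N and not above the other group. Item 3 fails, since 0 N lies outside both Table 1 ranges (25-100 N and 100-200 N). Item 4 fails, since neither group is higher. So they would.

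**3. Would item 2 catch a minority of failures?** Assumptions, not protocol figures: true means at the Table 1 midpoints, (100 + 200)/2 = 150 N and (25 + 100)/2 = 62.5 N; dead sensors read 0 N throughout; none fail in the no/mild group. With k of 14 moderate/severe sensors dead, the group mean is 150 × (14 - k)/14.

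| k | Mean (N) | Ratio to 62.5 N |
|---|---|---|
| 4 | 107.1 | 1.71 |
| 5 | 96.4 | 1.54 |
| 6 | 85.7 | 1.37 |
| 7 | 75.0 | 1.20 |

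The 100 N floor is kept up to k = 4, and the 25% excess up to k = 6. Counting those prototypes as failures would give 24/28 = 85.7% and 22/28 = 78.6%, both short of 90%.

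Range:
- True moderate/severe mean 125 N: the limits are k = 2 (floor) and k = 5 (excess). At 175 N they are 6 and 7.
- No/mild mean 50, 75 or 100 N, with 150 N in the other group: the limit for the 25% excess is 8, 5 or 2.
- Equal failure fractions in both groups leave the ratio at 150/62.5 = 2.4.
- Sensors that lose half their sensitivity: with 9 of 14 affected, the mean is 150 × (5 + 9 × 0.5)/14 = 101.8 N.

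**4. Items 3 and 4.** Item 3 looks at individual participants, but has no threshold and cannot separate a bad sensor from a wrong severity group. Item 4 uses the word accuracy but compares one group with the other, without a reference force.

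**5. Item 1 taken alone.** Let X be the number of passing prototypes, X ~ Bin(28, p), with pass probability P(X ≥ 26).
- Storage and transmission only, assumed p = 0.95, 0.98, 0.99: 0.837, 0.982, 0.997, whatever the state of the sensors.
- With a valid sensor also required, p = 0.98 × (1 - sensor failure rate): 0.342, 0.041 and 0.002 at failure rates of 10%, 20% and 30%.

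**6. Dilution of the 21-night average.** Assume 30% of sensors fail on a night uniform over 1 to 21 and read 0 N from that night on. Mean nights lost are 11 of 21, so the group mean falls by 0.30 × 11/21 = 15.7%. A participant with a true 125 N reads below 100 N when more than 20% of nights are lost, that is 5 or more, which means failure by night 17: 0.30 × 17/21 = 24.3%. If the failure night itself still reads correctly, the figures are 0.30 × 10/21 = 14.3% and 0.30 × 16/21 = 22.9%.

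**The case against.** The strongest reply is that item 1 is only one of four. Dividing the milestone into data handling (item 1) and force validity (items 2 to 4) is a reasonable structure, and the Aim 3 summary makes a similar division. Sensor failure pushes items 2 and 3 towards failing, so it does not help the pilot to succeed. The post-use calibration will show the team which devices have drifted. Acceptance limits and sensitivity analyses may also be left to an analysis plan that is not at hand.

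Much of this stands. A reader might infer from item 1 that a pilot in which every sensor had failed could be declared a success. The documents do not support that: items 2 to 4 need force readings and would then fail, and nothing in the text makes item 1 sufficient on its own. The binomial figures therefore describe item 1 only, under assumed reliabilities, and not the chance of meeting the whole milestone.

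The dilution figures also have a limit. The Data analysis paragraph averages compression force episodes, so a dead sensor may contribute no episodes instead of zeros; the protocol does not say which. In that case there is no dilution, but the dead sensor also drops out of the group mean, and item 2 does not register it.

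What the reply does not remove is that the success definition is fixed in the protocol itself, that no item sets an accuracy limit for a device, and that the one planned reference check after wear has no role in any of them.

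**Conclusion.** The point holds in this form. Item 1 counts a prototype as a success whether or not its sensor still responds, and items 2 to 4 make up for this only when failure is widespread. On the assumed means of 150 N and 62.5 N with 0 N readings from dead sensors, 4 of 14 moderate/severe sensors can be dead with the mean above 100 N, or 6 of 14 under the alternative of a 25% excess. Across the ranges tried, the limits run from 2 to 6 for the floor and from 2 to 8 for the excess. At the low end, 2 dead sensors would also be tolerated by the repaired rule, so the gap matters most when the true group means are well apart. The defect in the wording of item 1 depends on none of these assumptions. The text also does not say whether all four items must be met. The change should be made, though the gap does not invalidate the pilot.

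**What to change.** - Reword item 1 so that a prototype counts as a success only if it stores and transmits its data and, using its pre-use calibration, reads the known loads at the planned post-use calibration within a pre-stated margin. The sponsor sets the value; the Aim 1 margin of 10%-15% is the only accuracy milestone in the document.
- Use all issued prototypes as the denominator.
- Report the storage/transmission rate and the valid-sensor rate side by side.
- State that all four milestone items are required.
- Repeat the group force comparison without devices that fail the post-use check.

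The cost is a few sentences in the milestone and one sensitivity analysis. The calibration is already scheduled, so nothing new is measured. The drawback is that the reported success rate may be lower.
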